### Advanced molecular testing

Advanced molecular testing, such as PCR, viral loads, viral sequencing (sequencing the virus, not any human elements in the sample), or any testing we feel will help us optimize the assay, may be performed on any samples. The following will be used by the study team and can be shared with the scientific

community and the public through modes such as scientific publications and presentations as well as open research portals and online databases, such as GISAID:

- results of the sequencing, PCR or other molecular tests
- sample collection date and location
- sample collection county

GISAID is being used to collect all SARS-CoV-2 sequences and track the spread of the virus globally by the research community using the sequences of the viruses and when they are appearing in communities.

- This activity will not help the participant directly. The results will help researchers track the spread of the virus globally.
- Results of this activity will not be relayed back to the participant or put into their medical record.

Results of this study will be shared with the public via open research portals and online dashboards.

## 11.2 Assay Methodology

### Direct SARS-CoV-2 colorimetric RT-LAMP assays with heat-inactivated saliva samples

(Variations of this methodology and assay may be used in the optimization experiments and on-site/mobile testing.)

#### 1) Collection of ~1ml saliva samples after informed consent

- a. An individual will spit into a pipet tip that is placed inside a 1.5ml Eppendorf tube containing a label showing the participant's assigned ID.. The saliva will drain into the Eppendorf tube.
- b. The participant will close the tube, dispose of the tip (in biohazard waste when available) and then wipe the outside of the tube with a disinfectant wipe.
- c. If the participant is at a testing site, they will place the tube containing saliva in a rack inside a cooler that contains a cold pack. If they are collecting the sample at home or another location, they will store the tube at room temperature until taken to the drop box or testing site.
- d. The participant can dispose of the disinfectant wipe in a biohazard bin (if available) or in the trash and clean their hands with sanitizer or soap and water.
- e. Samples will be collected from the cooler or designated drop off site by study team members wearing proper PPE and transported to the testing location using approved UW transport methods.

#### 2) Behind Plexiglass or in a biological safety cabinet (BSC): (Wipe tubes with 10% bleach between movements)

- a. Place the tubes containing saliva in a thermomixer or dry bath at 65°C and shake for 30 minutes to inactivate the virus.
- b. Transfer samples to a thermomixer or dry bath at 98°C and shake if needed for 3 min to complete inactivation of virus particles and saliva nucleases.
- c. Spin the samples for 2 minutes in a benchtop centrifuge at 300 rpm.
- d. Dilute saliva into 1X PBS 1:1 and mix prior to adding to the LAMP reaction, or add saliva directly to the LAMP reaction with an equal volume of 1X PBS..

#### 3) Once these heating steps are complete, transfer the tubes with diluted, inactivated saliva to a cooler or refrigerator prior to setting up the colorimetric RT-LAMP reactions.

a. **Beyond this point, any potential SARS-CoV-2 particles in the saliva can be considered inactivated and could be handled without the plexiglass shield or outside of a BSC.**

4) While saliva samples are being heat inactivated, prepare the appropriate volume of the following Master Mix for the colorimetric RT-LAMP reactions:

Reagent	1X Rxn	9X Rxn	25X Rxn	100X Rxn
WarmStart Colorimetric LAMP 2X Master Mix (NEB, M1800L)	10 ul	90 ul	250 ul	1000 ul
dH 2 O	5 ul	45 ul	125 ul	500 ul
10X LAMP primer mix (ColorLAMP N)	2 ul	18 ul	50 ul	200 ul

5) Aliquot 17 ul of colorimetric RT-LAMP reaction mix into a fresh set(s) of PCR strip-cap tubes. Prepare samples in duplicate for each saliva sample. Hold these LAMP reaction tubes in a cooler prior to adding heat-inactivated saliva samples.

6) Add 3ul of heat-inactivated saliva (that is already diluted 1:1 in 1X PB) or add 1.5 ul of heat-inactivated saliva and 1.5ul of 1x PBS to the LAMP reaction. The final four positions in each batch of LAMP reaction strip-cap tubes should be reserved for two negative and two positive controls, respectively.

- The **negative control** reactions should contain 3 ul water/PBS.
- The **positive control** reactions should include 1000 copies of SARS-CoV-2 virus that has been inactivated by heat or UV irradiation. The vRNA is prepared in a 50:50 mix of water and 1X PBS to a concentration of 333 copies/ul so that we can add 3 ul to the positive control. With 1000 copies of vRNA in the positive control, this would equate to a saliva sample concentration of 666,666 copies of SARS-CoV-2 per ml of saliva. Thus, our assay will readily detect saliva containing a concentration of 10^6 copies of SARS-CoV-2 per ml.

7) Take a picture of the strip tubes before incubating the RT-LAMP reaction.

8) Incubate the colorimetric RT-LAMP reactions in a thermomixer or dry bath at 65°C for 30 minutes while shaking if needed.

9) Document any color changes at a 30-minute timepoint by digital photography of the RT-LAMP reactions against a prelabeled template on a white background. Color change from pink to yellow in both replicates is indicative of a sample with SARS-CoV-2 RNA present. If the color change to yellow is only clear in one of two replicate saliva samples, the sample will be scored as a potential finding of clinical significance.

10) Once a session of RT-LAMP testing is completed, disinfect all lab equipment with 10% bleach wipes followed by 70% EtOH spray. Collect all used pipet tips, plasticware, wipes, PPE, etc. in a biohazard

container and transport them back to AVRL to autoclave (if no autoclave is available at the site where samples are being processed) noting precautions for potential sharps on the autoclave bag. Saliva samples with evidence of SARS-CoV-2 RNA may be banked at AVRL at -80°C if the study participant has given appropriate consent to do so.

## 12.0 DATA COLLECTION, HANDLING, SHARING, AND RECORD KEEPING

### 12.1 Data Collection

#### 12.1.1 Data Collection Forms

Data collection is the responsibility of study team members under the supervision of the Principal Investigator (PI). The PI is responsible for ensuring the accuracy, completeness, legibility, and timeliness of the recorded and reported data.

Data being collected consists of the name of the person, the date and the county the sample was collected in. This information will be collected on the Consent form which will already have a participant ID associated with it. The ID will be assigned to that participant for the duration of the study. All forms must be completed in a legible manner; any missing data will be explained. Data entry errors will be corrected with a single line through the incorrect entry and the correct data is entered above/near the correction. All changes will be initialed and dated.

Data collection/consent forms are maintained in the subject files and retained as described in Section 12.3: Records Retention.

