## 7.0 STUDY DESIGN

### 7.1 General Design

We have developed a simple test to detect high concentrations of SARS-CoV-2 in saliva with assays that require no specialized equipment and can be completed in one hour. This assay is not diagnostic for SARS-CoV-2; instead, it specifically identifies saliva samples that have high amounts of viral RNA that are correlated with live virus shedding. Many samples that would be identified as SARS-CoV-2 by diagnostic qRT-PCR would be negative with our saliva assay. Conversely, detection of RNA in saliva is a potential finding of clinical significance, so individuals with that result will be contacted by a physician with appropriate expertise ([name]) to discuss potential follow-up with their own health care provider, including a possible independent diagnostic testing.

Because the assay requires no specialized equipment, it can be performed at the site of sample collection using a portable laboratory that fits in the backseat of a car. We intend to prototype testing in a variety of settings that may include parking lots, workplaces, nursing homes and residential housing. Participants will be asked to consent to provide a saliva sample that will be tested for SARS-CoV-2 RNA levels consistent with live virus shedding. The consent document will explicitly state that this is not a diagnostic test for SARS-CoV-2 but that a potential finding of clinical significance should be discussed with a medical professional. Participants can opt-out of receiving any results at the time of consent and can provide samples for the sole purpose of contributing to community surveillance and assay development. Paper consent forms will be reviewed and signed and held by team members in a secure location (locked box at the collection site) until taken back to the AIDS Vaccine Research Laboratory for storage. Participants will then spit into a coded vessel (e.g., cup or tube). Samples should be at least 1ml (~1/4 teaspoon) and will be assayed for the presence of SARS-CoV-2 RNA using the aforementioned detection assay; the presence of high concentrations of SARS-CoV-2 RNA is indicated by a colorimetric change from pink to yellow/orange.

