Results of all testing will be documented. The codes of the samples that indicate the presence of SARS-CoV-2 RNA will be given to [name] who will use the key to identify those participants. He will then contact them via phone with the finding of potential significance, encourage them to isolate and contact their healthcare provider for a possible diagnostic test. No results will be communicated to the employer of the participants. Parents will be contacted directly when giving results for all minors under 18 yrs of age.

The consent form will ask for name, date, county of sample collection and phone number. Samples may be banked for future use. Participants will have the opportunity to opt out of allowing their sample to be banked. As part of the study, participants must agree to have any virus found in their sample be sequenced. Virus that is sequenced will have the date and county of collection linked to it. This information will be shared with the scientific community via publications and presentations and online databases such as GISAID that is being used to collect all HCoV19/SARS-CoV-2 sequences and track the spread of the virus globally by the research community using the sequences of the viruses and when they are appearing in communities. By consenting, the participant will also be agreeing to allow us to perform advanced molecular testing on their sample to help answer critical questions and optimize the assay. We may also share their data and results of those additional tests with the scientific community and the public through publications, presentations, open research portals or other online databases.

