#### **12.4.7 Process for Returning Results**

The study team will contact [name] and let him know the code of the samples that had a potential finding of clinical significance and he will use the key to contact the corresponding participant. If [name] has not received the key yet for the testing done that day, a member of the study team (that is not in a supervisory role to the participants) will give him the names and phone numbers of the individuals (or their parent/legal guardian) that had a potential finding of clinical significance over the phone. [name] will contact the participant with the results and reiterate that the test is investigational and the results are not diagnostic. He will strongly recommend that the participant obtain a clinical diagnostic test for COVID-19 and practice self-isolation until the results of the test are received. [name] will also provide information about testing options.

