#### **12.4.8 Process for Tracking Subject Consent and Authorization**

The study team will create a spreadsheet to document which samples and data are allowed to be shared.

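### Do repeat samples lose their collection date and county because the plan names only the consent form as their source?

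*Combined protocol and SAP*

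**What the plan says.** Consent is taken at the first visit and not repeated, while sampling may continue without limit for as long as the study runs (sections 10.1.1 and 10.1.2). The version history shows that single consent and repeat testing came in with version 3.0.

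On records, section 12.1.1 states: "Data being collected consists of the name of the person, the date and the county the sample was collected in". It continues: "This information will be collected on the Consent form which will already have a participant ID associated with it". Section 7.1 agrees: "The consent form will ask for name, date, county of sample collection and phone number". The identifier belongs to the person: "The ID will be assigned to that participant for the duration of the study". Section 11.2, step 1, has the tube label show that identifier, and section 11.1 describes a vessel code that links back to the participant or the consent form.

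Other places speak of samples one by one. Section 7.1 has "Participants will then spit into a coded vessel" and "The codes of the samples that indicate the presence of SARS-CoV-2 RNA will be given to" a study physician. Section 12.4.7 has the team contact the physician and "let him know the code of the samples that had a potential finding of clinical significance". Section 12.4.8 provides for "a spreadsheet to document which samples and data are allowed to be shared".

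Section 12.2 keeps participant code, date, county and sequence together in electronic files. Sections 12.4.1 and 12.4.2 link those data to each banked sample.

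**The concern.** A form completed once can carry the date and county of one sample. Someone who gives several samples therefore has later tubes for which the visible text names no place where those items are first written down. The label rule mentions only a person-level identifier, so two tubes from one person might look alike. Participant code plus date would tell apart tubes from different days, but only if the later dates are recorded somewhere.

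What would be at stake is the information attached to repeat tubes that are banked or sequenced after their testing session. Samples may be held for up to 7 years and their data indefinitely (section 12.4.4). Date and county accompany sequences into public databases (sections 7.1, 11.1 and 12.1.2). If someone traced a stored repeat tube to the consent form and copied that date, the entry would look complete and be wrong. Home collection adds some doubt, because drop-off need not be the day or county of collection.

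**Working it through.** The plan gives no figure to reproduce. The check sets the sections side by side, followed by a bound on the date and a count.

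**1. What is missing.** For a participant with k samples, the consent form serves 1 and leaves k − 1 without a named source form. No visible section names a visit log, a drop-off log or an accession number. This part of the concern is correct.

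**2. What the plan requires all the same.**

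| Section | Requirement |
|---|---|
| 7.1 | Results of all tests are documented |
| 11.2, step 9 | Reactions are photographed against a template labelled beforehand |
| 12.2 | Code, date, county and sequence sit together in electronic files |
| 12.4.1, 12.4.2 | Date, location and county are stored with, and linked to, the banked sample |
| 12.4.4 | Those data are kept indefinitely |

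These duties cover repeat samples as much as first ones, and they can be met only if someone records each sample's date. The plan fixes the result and leaves the form unnamed. A date recorded at the session does not lapse when the tube goes into the freezer.

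**3. Whether any instruction produces an error.** No section tells staff to carry the consent date over to a later tube. Section 11.2 says what the label shows; it does not say that the label shows nothing else. A code linked to the participant, as in section 11.1, may still be specific to the sample. Identical labels are compatible with the text but not required by it.

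**4. How far out a session date could be.** Section 11.1 requires testing within 24 hours. Assume that the clock starts at collection. A tube collected on day D is then tested on D or D + 1, so the session date is wrong by 0 or 1 calendar day. Section 3.1 has drop-offs processed the same day, and section 11.1 sets fixed drop-off times. If the clock starts at drop-off instead, the time a tube spent at home is not bounded by this argument.

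**5. How many tubes.** With m the mean number of samples per person, the repeat share is 1 − 1/m. With f the fraction banked or sequenced later, taken as equal for first and repeat samples, the count per 10,000 samples is 10,000 × (1 − 1/m) × f. The documents give neither m nor f, so all values below are assumptions.

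| m | Repeat share | f = 1% | f = 10% |
|---|---|---|---|
| 1 | 1 − 1 = 0% | 0 | 0 |
| 1.25 | 1 − 0.80 = 20% | 20 | 200 |
| 2 | 1 − 0.50 = 50% | 50 | 500 |
| 5 | 1 − 0.20 = 80% | 80 | 800 |

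For example, m = 2 and f = 10% give 10,000 × 0.50 × 0.10 = 500. These are tubes whose date depends on a record the plan does not name. They are not tubes with a wrong date, so the table says nothing about an error rate.

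**6. What uses the date.** The endpoint in section 6.0 counts samples. Section 13.1 states no formal hypothesis, and section 13.4 plans no statistical methods. The exclusions in section 13.3 concern pipetting and contamination, which are noticed at the bench. Phoning a participant needs only the participant's identity. The synopsis aim of repeated testing over time needs an identifier that stays with the person, and section 12.1.1 provides one.

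**The case for a change.** The strongest case for a change is that the failure would be silent. The only named source returns the first visit's date for every later tube, that date looks valid, and it could enter a public database meant to show when viruses appear in a community. A date not captured at collection may be impossible to recover. The remedy would cost a label and one log line per sample.

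Some of this stands. The visible text does not name the source form. Participant code plus date would not separate two tubes given on the same day. For a tube collected at home, the county of drop-off may not be the county of collection, and no collection time is called for, so the 24-hour limit cannot be verified for such tubes.

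The harmful step does not stand. It needs staff to log no session date, although results are to be documented and date and county linked to the stored sample, and then to borrow a date from another visit. Nothing in the plan directs that. The low cost of a remedy does not show that the plan would go wrong without it.

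**Conclusion.** The observation is accurate as a description of sections 7.1, 11.2 and 12.1.1: their wording fits one sample per person and names no per-sample form. It does not call for a change. The plan already commits to linking date and county to stored samples, and a competent laboratory would log each tube's date to meet that commitment. Naming the log would only put an ordinary bench step on paper, and a laboratory procedure can do that.

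No stated endpoint or analysis would move. Calls to participants are unaffected, and exclusions can mostly be traced by session. On the reading that the 24 hours run from collection, a session date is at most one calendar day out. The number of tubes concerned cannot be derived from the documents.

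The conclusion assumes that the team keeps session dates with its documented results. The appendix forms listed in section 17.0 were not available, so a per-sample field there can be neither confirmed nor ruled out.

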#### 12.1.2 Data Management

The date and county of collection along with the viral sequence will be entered into spreadsheets for use in presentations, manuscripts and publications and online databases such as GISAID. The participant's name will not be put into spreadsheets or stored on any devices.

### 12.2 Confidentiality and Privacy

Subject confidentiality and privacy is strictly held in trust by the participating investigators, their staff, and the sponsor(s) and their agents. This confidentiality is extended to cover testing of biological samples. Therefore, the study protocol, documentation, data, and all other information generated will be held in strict confidence. No information concerning the study or the data will be released without consent of the participant. Participants may give consent to have the date and county of collection linked to viral sequencing done on their sample. This data will be shared through online databases, publications and presentations but because it will only be the sample collection date and county that is shared with the sequence of the virus found in their sample, there is a very minimal risk of being identified associated with the sharing of this data.

All research activities will be conducted in as private a setting as possible.

All study staff engaged in the conduct of this project have completed training on the protection of human subjects and the Health Insurance Portability and Accountability (HIPAA) Privacy Rule. In addition, all key personnel (i.e., Principal Investigator, individuals involved in identifying/recruiting subjects, obtaining informed consent, or interacting and intervening with subjects) have undergone Good Clinical Practice (GCP) training.

Information about study subjects will be kept confidential and managed according to HIPAA requirements. All subjects will sign a combined informed consent and HIPAA authorization form that includes specific

privacy and confidentiality rights. Study data will be maintained per federal, state, and institutional data policies.

The investigator(s) will ensure that the identities of subjects are protected by using coded subject information. The key where participant's identifying information is linked to their code on the consent form will be maintained by the investigator with a copy also being held by [name] or a physician with appropriate expertise on the study team. The key and all study records maintained at AVRL will be in a locked building with restricted access within a locked cabinet. A copy of the key will be kept by [name] or a physician with appropriate expertise on the study team and will be kept in a locked room or cabinet when not in use. The key will remain a hard copy vs electronic. Electronic study files containing the participant's code, date and county of collection and the viral sequences will be stored on the School of Medicine and Public Health, Department of Pathology and Laboratory Medicine servers and accessed via networked computers that are password-protected with access provided only to authorized study personnel. Consent forms will remain in paper form only.

Authorized representatives of the following groups may need to review this research as part of their responsibilities to protect research subjects: representatives of the IRB, regulatory agencies and federal oversight agencies, such as the Food and Drug Administration (FDA). The study team will permit access to such records.

Study staff may use email to communicate with site administrators, research subjects or their parents/legal guardians prior to consenting but information contained in the emails will be limited to answers to general questions about the study or confirm testing dates and times. All emails to subjects will be sent from UW/wisc.edu accounts; personal, home or Gmail email accounts will not be used.

To further protect the privacy of study subjects, a Certificate of Confidentiality has been obtained. This certificate protects identifiable research information from forced disclosure. It allows the investigator and others who have access to research records to refuse to disclose identifying information on research participation in any civil, criminal, administrative, legislative, or other proceeding, whether at the federal, state, or local level. By protecting researchers and institutions from being compelled to disclose information that would identify research subjects, Certificates of Confidentiality help achieve the research objectives and promote participation in studies by helping to assure confidentiality and privacy to subjects.

